8.6.4.9 Time to first normal testosterone level

Time to first normal total testosterone level will be analysed using the Kaplan-Meier method. As per Section 7.1.3.1, subjects that did not achieve testosterone normalisation (300-1000 ng/dL) or who discontinued the treatment period before achieving it will be considered as “censored” subjects. The number of subjects are normalised at baseline will be presented but excluded from the analysis.

For the following time points: Week 4, Week 8, Week 12, Week 16, Week 20 and Week 24 the number of subjects not having achieved a normal total testosterone value from baseline to the timepoint, the cumulative number of subjects who have achieved a normal total testosterone value at the end of the period and the probability of achieving a normal total testosterone level at the end of the period with the associate two-sided 95% CIs will be presented by treatment regimen. The point estimates and the relative two-sided 95% CIs will be presented by treatment regimen for the 75th, 50th and 25th percentiles. A Kaplan-Meier plot will also be presented. Comparisons between treatment regimens will be performed by means of the log-rank test.

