7 STATISTICAL CONSIDERATIONS AND ANALYSIS

7.1 Derived Variables

7.1.1 General Variables

Study Day

Study day will be relative to the date of first study medication (Study Day 1) and calculated as:

- (assessment date – date of first dose of study medication) + 1, for assessments on or after the date of first dose of study medication date
- (assessment date – date of first dose of study medication), for assessments prior to date of first dose of study medication

Follow-up time

Follow-up time (days) will be calculated as:

(date of last contact - date of first dose of study medication) + 1

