7.1.3 Definitions relative to efficacy criteria

7.1.3.1 Total Testosterone

Testosterone Normalisation

A subject is deemed to have achieved testosterone normalisation if their total testosterone value is between 300-1000 ng/dL (10.4-35 nmol/L) inclusive.

To allow for a potential 10-25% decrease in total testosterone that can occur due to diurnal variation in the afternoons (given current testing is restricted to mornings), a stricter secondary definition of normalisation will be used. A subject is deemed to have achieved the secondary definition of testosterone normalisation if their total testosterone value is between 350-1170 ng/dL (12.15-40.6 nmol/L) inclusive. The secondary definition boundaries were derived by averaging the testosterone value that a 25% decrease in would result in the primary definition boundary with the primary definition boundary itself.

Testosterone Overshoot

A subject is deemed to have testosterone overshoot if their total testosterone value is greater than 1000 ng/dL (35 nmol/L).

Time to first Testosterone Normalisation

Time to first Testosterone Normalisation is defined as the time (in days) from the date of first dose of study medication until the date of the first occurrence of testosterone normalisation during the treatment period.

Subjects who do not achieve testosterone normalisation will be censored at their final testosterone assessment during the treatment period (Up to Visit 8).

End of Treatment Testosterone

End of treatment testosterone is defined as the Week 24 total testosterone assessment for subjects that completed the treatment period. For subjects that discontinued the treatment period early, the last on-treatment testosterone assessment will be used as their end of treatment testosterone value.

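### Exact-day Kaplan-Meier for time to first normal testosterone overstates the end of the curve, and the SAP does not define the day behind each weekly row

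*SAP*

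**What the plan says.** SAP 7.1.3.1 defines the variable as "the time (in days) from the date of first dose of study medication until the date of the first occurrence of testosterone normalisation". Men who never reach the range "will be censored at their final testosterone assessment during the treatment period", that is, on their own visit date.

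SAP 8.6.4.9 then states: "Time to first normal total testosterone level will be analysed using the Kaplan-Meier method". It sets the rows of the table with the words "For the following time points: Week 4, Week 8, Week 12, Week 16, Week 20 and Week 24" and asks, for each, for the numbers not yet and cumulatively normalised and for "the probability of achieving a normal total testosterone level at the end of the period", with 95% confidence intervals. It also asks for the 25th, 50th and 75th percentiles, a plot and a log-rank test. Men already normal at baseline are left out.

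The schedule of assessments (Protocol Table 9-1) puts testosterone at Day 8 ±1 day and at Weeks 4 to 24, each ±2 days. The SAP has analysis windows for actigraphy (Appendix E) and DEXA (Appendix F) but none for testosterone. Nothing in 8.6.4.9 attaches a day number to a week or aligns event and censoring times to the scheduled visit.

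**The concern.** The data show only at which visit a man was first seen to be normal. His calendar day within the window reflects scheduling. Treating that day as an exact event or censoring time has two effects.

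- **End of the curve.** At the last visit, a non-normalised man seen on Day 166 is censored before a man seen at the same visit on Day 170 can have his event. The risk set shrinks within one visit, and the later events count too heavily.
- **Weekly rows.** If Week 4 is read at its nominal day, a man first normal at a Week 4 visit held one or two days later is missing from that row and first appears at Week 8.

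This is the only planned analysis of exploratory endpoint 12, and it bears on secondary objective 1, the time-course of normalisation. The background section of the protocol (7.1) reports normalisation within 2 to 4 weeks in the previous study, so the Week 4 row is the one most likely to be read.

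**Working it through.** **Inputs.** Time scale and censoring rule: SAP 7.1.3.1. Method and rows: SAP 8.6.4.9. Windows: Protocol Table 9-1. Group size: 67 (SAP section 5). The documents give no per-visit normalisation rates and no distribution of visit days, so both are assumptions here.

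**The plan's own figure.** The plan states no figure for this analysis. The 67 per group is reproduced by the normal approximation for 75% against 90% at one-sided 2.5% and 85% power: 59.8, or 66.3 with continuity correction, rounded up to 67.

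**End of the curve, exact arithmetic.** Spread the Week 24 visits evenly over five days and let a share h of the men still at risk normalise at that visit. The share still at risk falls by a fifth each day, so the visit contributes

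1 − (1 − h/5)(1 − h/4)(1 − h/3)(1 − h/2)(1 − h)

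instead of h. This gives 11.0% for h = 5%, 21.0% for h = 10% and 38.7% for h = 20%. In a group of 67:

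| At risk entering Week 24 | First normal at Week 24 | True cumulative share | Curve at Day 168 | Day 169 | End (Day 170) |
|---|---|---|---|---|---|
| 60 | 5 | 12/67 = 17.9% | 16.2% | 19.7% | 26.4% |
| 20 | 5 | 52/67 = 77.6% | 75.6% | 78.7% | 84.0% |

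First row: (60/67) × (59/60)(47/48)(35/36)(23/24)(11/12) = 0.736, so the curve ends at 26.4%, which is 8.5 points too high.

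**End of the curve, simulation (67 men per arm).**

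- Placebo-like arm, per-visit rates .05, .08, .08, .08, .08, .08, .10: 44% ever normal, curve ends at about 51% under every day count and visit spread tried.
- Active-like arm, rates .35, .60, .40, .30, .20, .20, .20: 94.4% against 95.5%.
- Other assumed rates: 0.6 to 1 point in a fast active arm, about 3 points in a slower one (82.2% against 85.4%), 3 to 8 points in low-response arms.

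**Week 4 row.** With the active-like rates, 35% normalise at Day 8 and a further 0.65 × 60% = 39% at Week 4, so 74% by visit. If a share L of the Week 4 events falls after the day that is read, the curve shows 35% + (1 − L) × 39%. Clustered means 60% of visits on the nominal day and 10% on each of the other four.

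| Visit spread and day read | L | Curve | Shortfall |
|---|---|---|---|
| Any spread, read at window end | 0 | 74.0% | 0 |
| Clustered, count shifted one day | 10% | 70.1% | 3.9 |
| Clustered, nominal day | 20% | 66.2% | 7.8 |
| Even, count shifted one day | 20% | 66.2% | 7.8 |
| Even, centred on and read at 28 elapsed days | 40% | 58.4% | 15.6 |
| Even, one day added to the time | 60% | 50.6% | 23.4 |

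Simulation agrees: about 66% for each 20% case, 59% for 40% and 51% for 60%.

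The one-day shift is a genuine ambiguity. Visit 2 on Day 8 is seven days after first dose, and counting the same way makes Week 4 Day 29. Appendix F sets Week 24 at Day 168 = 7 × 24, which makes Week 4 Day 28, or 27 elapsed days. Study day in SAP 7.1.1 adds one; the definition in 7.1.3.1 does not.

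**Later rows.** The shortfall fades. In the second set of rates (even spread, no dropout) the fast active arm shows 65.0% against 78.0% at Week 4 but 90.3% against 91.0% at Week 20. At Week 24 the two distortions compete: in the first table Day 168 reads low and Day 169 reads high.

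**Log-rank test.** With 67 per arm and 1,500 replicates, exact-day and visit-indexed times gave type I error of 5.1% and 4.9% in one scenario and 5.4% and 4.9% in another. Power was 27.7% and 26.9%, then 41.9% and 42.2%.

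**The case against.** - **The read-off day is not documented.** Read at the end of each window, the rows are correct from Week 4 to Week 20. This stands: the weekly understatement is conditional. What is certain is that the SAP leaves the day open, and that the choice moves Week 4 by many points.
- **Even spread is unfavourable.** Hormone samples are taken before a weekly dose, which favours visits near the nominal day. This also stands. Clustering halves the Week 4 shortfall, but it did not reduce the overstatement at the end in the placebo-like arm.
- **The end of the curve lies mostly outside the table.** True if Week 24 is read at Day 168. It still appears in the plot and in any percentile reached there. In the placebo-like arm, 44% ever normalise while the curve ends near 51%, so a median time could be reported although fewer than half the men normalised.
- **The time-course is shown elsewhere.** SAP 8.6.2 gives the proportion normal at each visit and 8.6.3.2 a repeated-measures model. These answer much of secondary objective 1. They show status at a visit, not cumulative first normalisation, so they do not replace this analysis.
- **Exact-day Kaplan-Meier is common practice for visit-assessed outcomes, and the endpoint is exploratory.** Both true. This lowers the priority but does not make the estimate right.

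A reader might go further and infer that every weekly row is understated, that the log-rank comparison is biased, or that the lack of a Day 8 row is a defect. The documents do not support these. The direction at Week 24 depends on the day count. The windows are the same in all arms, and the simulation showed no material effect on the test. Day 8 events still enter the curve and the percentiles, so that row is a matter of layout.

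**Conclusion.** The concern holds in limited form. Applying the stated rule overstates the end of the curve: about 7 to 9 points in a placebo-like arm (51% against 44% in simulation, 26.4% against 17.9% in the worked example) and about 1 point in an active-like arm. Low-response arms under other assumed rates gave 3 to 8 points, and a slower active arm about 3.

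The understatement of the weekly rows depends on a read-off day the SAP does not give. It falls mainly on Week 4 in active arms: none at the window end, about 8 points with clustered visits or a one-day shift, 15 to 16 with even visits read at 28 elapsed days.

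All sizes rest on assumed rates and visit spreads. If every visit fell on its nominal day and the row were read there, both effects would vanish. The primary endpoint, sample size and interim analysis are untouched. This is a cheap improvement to an exploratory analysis.

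**What to change.** In SAP 7.1.3.1 and 8.6.4.9, assign each on-treatment testosterone assessment to a scheduled visit (Day 8, Weeks 4 to 24) and use that visit's nominal time for both events and censoring, in the table, the percentiles and the plot. Kaplan-Meier counts events before censorings at tied times, so both distortions disappear. A discrete-time or interval-censored (Turnbull) estimate would serve equally well.

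State the testosterone windows, as Appendices E and F do for actigraphy and DEXA. Assign early end-of-treatment visits by actual day: they carry the Visit 8 label but can fall well before Week 24 (Protocol 9.3.7).

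A Day 8 row is optional. The log-rank test need not change on present evidence.

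The cost is SAP wording and a few lines of code, with no new data. Times would be reported to the visit instead of the day, which is all the precision the data contain.

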8.7 Safety analyses

All definitions relative to safety endpoints are detailed in Section 7.1.4.

All safety analyses will be based on the Safety population and will be performed for all safety variables specified below.

No statistical tests will be performed.

8.7.1 Adverse events

All AEs will be classified by SOC and PT according to the MedDRA Version 19.1 or higher.

Details for imputing missing or partial start dates of adverse events are described in Section 7.2.2.4.

All AE summaries will be generated by treatment period, follow-up period and overall (i.e including those that started in both the treatment period and follow-up period).

Notes:

- Two AEs with the same PT will be considered as two different events when calculating the “number of events” in the tables.

- Where a subject has the same AE, based on preferred terminology, reported multiple times in the same category the subject will only be counted once at the preferred terminology level in AE frequency tables.
- Where a subject has multiple AEs within the same SOC in the same category, the subject will only be counted once at the SOC level in AE frequency tables.
- AEs where the intensity is missing will be assumed to be “Severe”
- AEs where the causality is missing will be assumed to have “Reasonable possibility of relatedness”

An overall summary of AEs will be provided. The total number of events and number and proportion of subjects experiencing any AEs, TEAEs, TEAEs of special interest, AEs related to study medication (i.e where the investigator has recorded “Reasonable possibility of relatedness”), SAEs, SAEs related to study medication, severe AEs, AEs leading to permanent discontinuation of study treatment and AEs leading to death will be tabulated for each treatment regimen and overall.

Additionally, TEAEs, TEAEs of special interest, related TEAEs, serious TEAEs, related SAEs, AEs leading to permanent discontinuation of study treatment and AEs leading to death will be summarised by SOC and PT for each treatment regimen and overall (number and percentage of subjects experiencing at least one AE per PT as well as the number of observed events per PT). All TEAEs will also be summarised separately by maximum intensity for each SOC and PT and by causality for each SOC and PT.

A table presenting the number and percentage of subjects with at least one AE and the number of AEs for the most common treatment-emergent AEs (reported in $\geq 1\%$ of patients in any treatment regimen) will be provided. PTs will be used for tabulation, sorted by decreasing overall frequency.

All AEs will be presented in full in a comprehensive listing including subject number, treatment regimen, intensity, seriousness, actions taken, outcome, causality, onset/stop and duration. Details of all TEAEs of special interest, SAEs, AEs leading to permanent discontinuation of study treatment and AEs leading to death will be listed separately.

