12.1.2 Recording of Adverse Events

For the purposes of this study, only SAEs will be collected during Screening Period (the time between signing the ICF and randomisation).

Any detrimental change in the subject's condition, after randomisation and up to 90 days after the last administration of study drug should be considered an AE.

The following variables will be recorded for each AE: verbatim/AE description and date for AE start and stop, severity, seriousness, causality rating, whether or not the AE caused the subject to discontinue, and the outcome. If the severity of the AE changes, a new AE must be recorded.

SAEs and AEs will be recorded after randomisation. SAEs only will be reported during the screening period (from signing of the informed consent to randomisation). All AEs/SAEs

have to be reported, whether or not considered causally related to the investigational product or to the study procedure(s).

All ongoing AEs/SAEs should be followed up until resolution or stabilisation or the last visit if in the investigator's opinion, the AE is unlikely to resolve due to the subject's underlying disease.

At any time after the FU visit, if an investigator learns of an SAE that can be reasonably related to study drug, he/she should promptly notify the sponsor.

Intensity

The investigator will assess the intensity of AEs based on the following definitions:

1. Mild (awareness of sign or symptom, but easily tolerated)
2. Moderate (discomfort sufficient to cause interference with normal activities)
3. Severe (incapacitating, with inability to perform normal activities).

It is important to distinguish between serious and severe AEs. Severity is a measure of intensity whereas seriousness is defined by the criteria in [Section 12.1.8](#).

An AE of severe intensity need not necessarily be considered serious. For example, nausea that persists for several hours may be considered severe nausea, but not an SAE. On the other hand, a stroke that results in only a limited degree of disability may be considered a mild stroke but would be an SAE.

For an AE to be a suspected drug-related event there should be at least a reasonable possibility of a causal relationship between the study drug and the AE.

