7.1.4 Definitions relative to safety parameters

7.1.4.1 Adverse Event (AE)

Treatment Emergent Adverse Event (TEAE)

A Treatment Emergent AE (TEAE) is defined as an AE occurring or worsening on or after the first dose of study medication. For subjects that enter the extension study, only AE's occurring prior to entering the extension study will be considered a TEAE and summarised.

TEAEs will also be split between AEs that start during the treatment period and those that start on or after the first day of the follow-up period (for subjects not entering the extension study).

Duration of AEs

The duration of an AE will be calculated as the resolution date minus the start date plus 1.

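### One continuous adverse event that changes severity is counted as several events, and one that only eases after Visit 8 can appear as a new follow-up TEAE

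*SAP*

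**What the plan says.** **Recording.** Protocol 12.1.2 states: "If the severity of the AE changes, a new AE must be recorded". The instruction is mandatory and is not limited to worsening. The same section gives every record its own dates: "The following variables will be recorded for each AE: verbatim/AE description and date for AE start and stop".

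**Counting events.** SAP 8.7.1: "Two AEs with the same PT will be considered as two different events when calculating the" number of events. That number is shown in the overall AE summary, the SOC and PT tables, and the table of most common TEAEs.

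**Counting subjects.** For a repeated PT in the same category, SAP 8.7.1 says "the subject will only be counted once at the preferred terminology level in AE frequency tables".

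**Periods.** SAP 8.7.1: "All AE summaries will be generated by treatment period, follow-up period and overall". SAP 7.1.4.1 sets the allocation: "TEAEs will also be split between AEs that start during the treatment period and those that start on or after the first day" of follow-up. The follow-up part applies only to men who do not enter the extension study.

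**Duration.** SAP 7.1.4.1: "The duration of an AE will be calculated as the resolution date minus the start date plus 1". Duration is shown in the comprehensive AE listing.

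**Protocol counting rule.** Protocol 13.5.5 counts a PT that recurs in a subject once, at its greatest severity. It also asks for the number of observed events per PT.

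**The concern.** The recording rule turns one clinical episode into a chain of records. The counting rule and the period rule then treat each link as an event in its own right. No section of either document links successive records or carries the first onset date forward. SAP 7.2.2.4, the only other text on classifying AEs by date, deals with incomplete dates.

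Two outputs are at stake. The first is the number of events per PT, which would partly measure how often severity was regraded. The second is the follow-up tables. Under SAP 8.9 the off-treatment data are analysed separately and published in an addendum, so those tables may be read on their own. An AE that started on treatment and was improving would appear there as an event arising off treatment.

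**Working it through.** The plan gives no figure on this point, so there is none to reproduce. The check follows the written rules through worked examples.

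**Inputs**
- A new record at each severity change, with its own start and stop dates (Protocol 12.1.2).
- Each same-PT record is one event (SAP 8.7.1).
- Period set by the record's start date (SAP 7.1.4.1).
- Visit 8 on Day 168, the Week 24 target day in SAP Appendix F.
- Assumed: the new record starts on the day severity changed, all records code to the same PT, and the man does not enter the extension.

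**Formula.** Events counted for one episode = k + 1, where k is the number of severity changes.

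**Example A.** Severe from Day 150, easing to mild on Day 175. Here k = 1, so 1 + 1 = 2 events. Day 150 is before Day 168 and Day 175 is after it, giving one treatment-period event and one follow-up TEAE.

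**Example B.** Mild, moderate, severe, moderate, mild, starting on Days 100, 120, 140, 160 and 180. Here k = 4, so 4 + 1 = 5 events. Four start by Day 168 and one after it.

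| | Example A | Example B |
|---|---|---|
| Clinical episodes | 1 | 1 |
| Events counted as written | 2 | 5 |
| of which treatment period | 1 | 4 |
| of which follow-up | 1 | 1 |
| Subjects, overall table | 1 | 1 |
| Subjects, follow-up table | 1 | 1 |
| Maximum intensity, overall | severe | severe |
| Events if records are joined | 1 (treatment) | 1 (treatment) |

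The overall subject count and the overall maximum intensity are right in both examples. The event count is not, and the follow-up table gains a man whose AE only improved in that period (unless he has another follow-up TEAE in the same row).

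**Duration.** In Example A, if the first record is closed on Day 175 its listed duration is 175 − 150 + 1 = 26 days, however long the whole episode lasted. The remainder is listed as a second AE.

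**Trial-wide size.** Inflation factor = 1 + (share of episodes that change severity) × (changes per such episode). Neither quantity is in the documents, so these inputs are assumptions:
- 5% with one change: 1 + 0.05 × 1 = 1.05
- 20% with one change: 1 + 0.20 × 1 = 1.20
- 30% with two changes: 1 + 0.30 × 2 = 1.60

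**The case against.** **The outputs most readers use are protected.** This stands. Overall incidence by SOC and PT and overall maximum intensity rest on one count per subject. SAP 8.7 plans no tests on AEs. The protection does not reach the number of events, and it does not stop a man counted in the treatment table from also being counted in the follow-up table.

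**Protocol 13.5.5 already counts a repeated PT once.** This stands in part. The same section also reports observed events per PT, and SAP 8.7.1 counts same-PT records separately for that number. The rule therefore leaves an ambiguity to reconcile and does not cure the count.

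**Easing is not an adverse event.** Protocol 12.1.2 describes an AE as "Any detrimental change in the subject's condition, after randomisation and up to 90 days" after the last dose, and improvement is neither detrimental nor a worsening. That may well be the intention. But the severity rule in the same section has no such limit, and a TEAE is one that occurs or worsens after first dose. A program working from start dates would class the new record as occurring.

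**The start date of the new record is inferred.** This stands. The CRF completion instructions and the table templates are not among the documents.

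A reader might also infer stronger points that the documents do not support:
- *Every grade change after Visit 8 creates a false follow-up TEAE.* A worsening falls within the TEAE definition; only easing is misplaced.
- *Pre-dose AEs become treatment-emergent in the same way.* Randomisation and first dose are both scheduled on Day 1, and only SAEs are collected before randomisation, so the window for ordinary AEs is normally part of one day.
- *Every AE table is wrong.* Event counts change only for PTs with a split episode. Duration is shown only in the listing, where onset, stop and intensity let a reader see contiguous records.
- *The inflation differs by arm.* Protocol 9.2.1 lists headache, sweats and musculoskeletal pain as common, but says nothing about fluctuating severity. Separate headaches are properly separate events.

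**Conclusion.** The point holds, as a gap in the derivation of descriptive safety tables. Followed as written, the plan counts an episode with k severity changes as k + 1 events. For men not entering the extension, it can tabulate an AE that started on treatment and only eased after Visit 8 as a follow-up TEAE. This rests on the new record starting on the date of the change and on its coding to the same PT.

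The trial-wide effect cannot be determined from the documents; the factors of 1.05 to 1.60 above only illustrate the formula. The follow-up effect is narrowed further because a minimum of 25 men per arm are to be invited into the extension, and those who enter have no follow-up period in this study. The efficacy analyses are not touched. The change is still worth making, because it alters tabulated numbers and the follow-up tables are reported separately.

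**What to change.** In SAP 7.1.4.1 and 8.7.1, add a derivation step:

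1. Join records of the same subject and PT that are contiguous in time into one event, with the onset of the first record, the resolution of the last and the maximum severity. Count it once and compute its duration from those dates.
2. Define contiguity, for example the stop date equal to, or one day before, the next start date. Records separated by a longer gap remain separate events.
3. Assign the period by the first onset. Count the event again in follow-up only if its severity rises above the level it had before follow-up began.
4. Reconcile this with Protocol 13.5.5 by stating that its once-only rule governs subject counts and that the observed-event count uses joined events.

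The individual records can stay in the listing, so nothing is lost. The cost is a paragraph of SAP wording and one programming step. The downside is that the result depends on the chosen contiguity rule, which should be fixed before unblinding. No new data are needed.
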